2.2. Study Objective(s) and Endpoint(s)

Objectives	Endpoints
Primary Objectives	Primary Endpoints
1) To assess the frequency and phenotype of leukocyte subsets in iLN and peripheral blood in HVs and NOT1D subjects	
 Absolute number and/or proportion of leukocyte subsets in iLN and peripheral blood
Secondary Objectives	Secondary Endpoints
1) To assess the frequency and phenotype of leukocyte subsets in iLN core biopsies and iLN fine needle aspirates in HVs and NOT1D subjects	
 Absolute number and/or proportion of leukocyte subsets in iLN core biopsies and iLN fine needle aspirates
2) To assess the safety and tolerability of iLN biopsy as well as expectations and experience of the biopsy procedure	
 Number of AEs and SAEs following lymph node biopsy procedure Descriptive data obtained by a questionnaire on the acceptability of iLN biopsy in research setting.
Exploratory Objectives*	Exploratory Endpoints
1) To assess suppression activity of T regulatory lymphocytes from the iLN and peripheral blood in HVs and NOT1D subjects	
 Relative levels of T lymphocyte suppressive activity of cells from iLN and peripheral blood respectively
2) To assess the frequency of cytokine-producing lymphocytes in HVs and NOT1D subjects	
 Proportion of lymphocyte populations producing pro-inflammatory and/or anti-inflammatory cytokines in iLN and peripheral blood
3) To assess clonal expansion of T and B lymphocyte populations in HVs and NOT1D subjects	
 Comparison of TCR and BCR usage in lymphocytes in iLN and peripheral blood
4) To assess the gene expression fingerprint of auto-antigen specific lymphocytes in HVs and NOT1D subjects	
 Gene expression levels of sorted auto antigen stimulated T lymphocyte populations in iLN and peripheral blood
5) To assess the phenotype and transcriptomic fingerprint of stromal cells from iLN core biopsy samples in HVs and NOT1D subjects	
 Absolute number and/or proportion of stromal cell subsets and gene expression levels of stromal cell subsets from iLN core biopsy samples

* The Exploratory objectives / endpoints are listed in order of priority and the conduct of any experimental assays will be dependent on the material available (i.e. number of cells obtained) from iLN biopsies and peripheral blood.

2.3. Study Design

Overview of Study Design and Key Features				
T1D Diagnosis (N.B. "T1D diagnosis" is not applicable to healthy volunteers)				
Screening Period	Study Visit	Follow Up Period 1	Follow Up Period 2	
Day ~ -42 to Day -7	Day 1: lymph node biopsy & blood collection	Day ~2 to Day ~4	Day ~7 to Day ~14	
Design Features	A multi-centre, non-drug treatment study to compare differences in immune cells derived from iLN and peripheral blood of NOT1D subjects and HVs.			
Dosing	
 Not applicable (non-drug interventional study) 			
Treatment Assignment	
 Not applicable 			
Interim Analysis	Interim analyses will be carried out at the following timepoints: 
 After at least 5 HVs have been biopsied. An interim analysis will be carried out after the recruitment of 5 evaluable HVs and 5 evaluable NOT1D subjects. These are further described in Section 3.1.			

2.4. Statistical Hypotheses

This study is designed to explore the phenotype of immune cells in the iLN and peripheral blood (such as, but not restricted to PBMCs) of NOT1D subjects compared to HVs.

There are no formal hypotheses being tested due to the exploratory nature of the study. Primary comparisons of NOT1D subjects to HVs will be made using an estimation approach, providing point estimates and confidence intervals.

Secondary comparisons of biopsy methods will be made within NOT1D subjects and HVs using an estimation approach:

[figure not shown]
- iLN biopsies will be carried out by two related methods, fine-needle aspirate (FNA) and core biopsy sampling:
- If sufficient numbers of cells to meet the cell number requirements of the primary endpoint are obtained by both biopsy methods, the primary endpoint analysis will be carried out independently for each biopsy method, otherwise only the biopsy

method for which sufficient numbers of cells were obtained will be used for primary analysis.

- If no meaningful differences between biopsy methods are observed, material from both biopsy methods may be pooled to meet exploratory objectives 1, 2, 3 and 4. Material from fine-needle aspirate and core biopsies will not be pooled unless supported by the comparison described above.
- If meaningful differences in the proportion of leukocyte subsets between cells derived from each biopsy method are observed, then:
 - If sufficient number of core biopsy derived cells are available, these will be analysed for exploratory objectives 1 and 2.
 - Fine needle aspirate derived cells will be used to meet exploratory objectives 3 and 4. If insufficient number of core biopsy derived cells are available to meet exploratory objectives 1 and 2, then fine needle aspirate derived cells may be used to meet either or both of those exploratory objectives.

A graphical representation of the comparisons are shown in [Figure 1](#).

Figure 1 - Graphical representation of comparisons

3. PLANNED ANALYSES

3.1. Interim Analyses

3.1.1. Interim Analysis 1

A data look will be carried after the recruitment of a cohort of up to 5 HVs to determine if the quality and quantity of cells derived from either fine needle aspirate or core biopsy of the inguinal lymph node and from peripheral blood are likely to be sufficient to continue the study to meet its primary objective.

The decision rules for the study to continue are:

- Peripheral blood yields $> 1 \times 10^6$ cells, and
- Yield from either iLN biopsy samples $> 1 \times 10^6$ cells.

In addition, the data from the interim analysis will be used to explore the assumptions and feasibility of the primary statistical analysis, and may also be used for pre-programming of outputs for the final analysis.

If the decision is taken to stop the study at the interim, the full safety outputs plus listings of other collected data will be produced.

3.1.2. Interim Analysis 2

An interim analysis will be carried out after the recruitment of 5 evaluable HVs and 5 evaluable NOT1D subjects. The primary purpose of this interim analysis will be to facilitate decision making and study design for a potential follow-up interventional study.

In addition, the interim analysis results would also help to enable prioritization of the exploratory assays and to facilitate the final RAP. Due to uncertainty around variability and precision, the primary analyses described in Section 7 will be performed in order to re-assess the precision of estimates for the comparisons of interest.

3.2. Final Analyses

The final planned primary analyses will be performed after the completion of the following sequential steps:

1. All subjects have completed the study as defined in the protocol
2. All required database cleaning activities have been completed and final database release and database freeze has been declared by Data Management.

4. ANALYSIS POPULATIONS

Population	Definition / Criteria	Analyses Evaluated
Screened	
 All participants who were screened for eligibility 	
 Study Population
Enrolled	
 All participants who passed screening and entered the study 	
 Study Population
Safety	
 Comprised of all subjects who complete any study assessment 	
 Study Population Safety
Core Biopsy	
 Subjects in the 'Safety' population for whom at least one lymph node core biopsy was taken 	
 Biomarker
Fine needle aspirate Biopsy	
 Subjects in the 'Safety' population for whom at least one lymph node fine needle aspirate biopsy was taken 	
 Biomarker
Biopsy	
 Subjects in both 'Core Biopsy' and 'fine needle aspirate biopsy' populations 	
 Biomarker
Blood	
 Subjects in the 'Safety' population for whom one blood sample was taken for analysis of cells derived from peripheral blood. 	
 Biomarker
Per Protocol	
 Subjects in the 'Safety' Population who were compliant with the Protocol 	
 Biomarker

NOTES :

- Please refer to [Appendix 10: List of Data Displays](#) which details the population to be used for each displays being generated.

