5.3. Screening/Baseline/Run-in Failures

Screen failures are defined as subjects who consent to participate in the clinical trial but did not undergo the study procedures (iLN biopsy and peripheral blood collection). In order to ensure transparent reporting of screen failure subjects, meet the Consolidated Standards of Reporting Trials (CONSORT) publishing requirements, and respond to queries from Regulatory authorities, a minimal set of screen failure information is required including Demography, Screen Failure details, Eligibility Criteria, and Serious Adverse Events (see Section [6.7.1.5](#)).

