6. STUDY ASSESSMENTS AND PROCEDURES

Protocol waivers or exemptions are not allowed with the exception of immediate safety concerns. Therefore, adherence to the study design requirements, including those specified in the Time and Events Table, are essential and required for study conduct.

[figure not shown]
This section lists the procedures and parameters of each planned study assessment. The timing of each assessment is listed in the Time and Events Table Section 6.1

- The change in timing or addition of time points for any planned study assessments must be documented in a Note to File which is approved by the relevant GSK study team member and then archived in the study sponsor and site study files, but this will not constitute a protocol amendment.
- The IRB/IEC will be informed of any safety issues that require alteration of the safety monitoring scheme or amendment of the Informed Consent Form.
- No more than 500 mL of blood will be collected over the duration of the study, including any extra assessments that may be required.

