6.2. Screening and Critical Baseline Assessments

The following demographic parameters will be captured: year of birth, sex, race and ethnicity.

Medical/medication/family history will be assessed as related to the inclusion/exclusion criteria listed in Section 5.

Procedures conducted as part of the subject's routine clinical management, for example but not limited to laboratory assessment, and obtained prior to signing of informed consent may be utilized for Screening or baseline purposes provided the procedure(s) meet(s) the protocol-defined criteria and has (have) been performed within the timeframe of the study.

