6.7.1.1. Time period and Frequency for collecting AE and SAE information

- Any SAEs assessed as related to study participation (e.g., protocol-mandated procedures, invasive tests) will be recorded from the time a subject consents to participate in the study up to and including any follow-up contact.
- AEs will be collected from: the start of study procedures until the follow-up contact (see Section 6.7.1.3), at the time points specified in the Time and Events Table (see Section 6.1).
- Medical occurrences that begin prior to the start of study procedure but after obtaining informed consent may be recorded on the Medical History/Current Medical Conditions section of the CRF.
- All SAEs will be recorded and reported to GSK within 24 hours, as indicated in [Appendix 3](#).

- Investigators are not obligated to actively seek AEs or SAEs in former study subjects. However, if the investigator learns of any SAE, including a death, at any time after a subject has been discharged from the study, and he/she considers the event reasonably related to the study procedures or study participation, the investigator must promptly notify GSK.

NOTE: The method of recording, evaluating and assessing causality of AEs and SAEs plus procedures for completing and transmitting SAE reports to GSK are provided in [Appendix 3](#).

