7. DATA MANAGEMENT

- For this study, subject data will be entered into GSK defined CRFs, transmitted electronically to GSK or designee and combined with data provided from other sources in a validated data system.
- Management of clinical data will be performed in accordance with applicable GSK standards and data cleaning procedures to ensure the integrity of the data, e.g., removing errors and inconsistencies in the data.
- Adverse events and concomitant medications terms will be coded using MedDRA (Medical Dictionary for Regulatory Activities) and an internal validated medication dictionary, GSKDrug.
- CRFs (including queries and audit trails) will be retained by GSK, and copies will be sent to the investigator to maintain as the investigator copy. Subject initials or other Personally Identifiable Information (PII) will not be collected or transmitted to GSK according to GSK policy.
- Screen failure information will be entered in to the clinical database (see also Section [5.3](#))

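### As written, the Safety population includes any screen failure who completed a screening assessment; if there are any, the AE percentages and Table 1.05 use the wrong denominator.

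*SAP*

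**What the plan says.** The final SAP (section 4) defines Safety as "Comprised of all subjects who complete any study assessment". Protocol section 8.3.1 and the SAP for the interim analysis use the same rule. The final SAP also has Screened and Enrolled populations, but does not make Safety a subset of Enrolled.

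Protocol section 5.3 states: "Screen failures are defined as subjects who consent to participate in the clinical trial but did not undergo the study procedures". In parentheses it names those procedures as the lymph node biopsy and peripheral blood collection. For these subjects, "a minimal set of screen failure information is required including Demography, Screen Failure details, Eligibility Criteria, and Serious Adverse Events". Section 7 adds: "Screen failure information will be entered in to the clinical database".

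On event collection, protocol section 6.7.1.1 says "AEs will be collected from: the start of study procedures until the follow-up contact". SAEs judged related to participation are treated differently: they "will be recorded from the time a subject consents to participate in the study up to and including any follow-up contact".

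Final SAP section 8 puts the safety analyses on Safety by default. Appendix 10 gives Safety as the population for Tables 3.01 to 3.05 (adverse events) and Table 1.05 (demographic characteristics).

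**The concern.** A secondary objective is the safety and tolerability of inguinal lymph node biopsy. A percentage meant to describe what happens after the procedure should have as its denominator the people exposed to the Day 1 procedures. The written rule also counts people who were screened, failed and went no further. They normally cannot contribute a non-serious AE, so they enlarge the denominator and leave the numerator alone. The resulting percentages make the biopsy look better tolerated than it was.

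Table 1.05 has a related problem. It should describe the people whose samples are compared, in a study that seeks to match the groups on gender and on age within gender. As written, it could include people who gave no cells for any comparison.

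**Working it through.** **Step 1: do screening items count as study assessments?** Protocol section 6 opens by saying "This section lists the procedures and parameters of each planned study assessment" and refers to the Time and Events Table for timing. That table has a screening column with physical examination, medical history, laboratory tests and vital signs. Section 6.2, whose heading itself calls the screening items assessments, says "The following demographic parameters will be captured: year of birth, sex, race and ethnicity". A screen failure with any of these completed meets the Safety rule.

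**Step 2: does anything remove them later?** No section of either document limits Safety to enrolled, sampled or biopsied subjects. The Core Biopsy, Fine Needle Aspirate, Blood and Per Protocol populations are each defined as Safety plus a condition, so the authors nest populations where they mean to.

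**Step 3: size.** The plan gives no AE percentage to reproduce. Let n be subjects with a Day 1 procedure and s the screen failures counted in Safety. With no non-serious AEs among screen failures:

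reported % = true % × n/(n+s)

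Inputs:
- n = 30, from up to 15 evaluable subjects per group (protocol section 4.2).
- True rate 80%, the upper haematoma figure cited in protocol section 4.4.1, used only as an illustration (24 of 30).
- s is not in the documents. The values below are assumptions.

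| s | n/(n+s) | a true 80% is shown as |
|---|---|---|
| 0 | 30/30 = 1 | 80% |
| 5 | 30/35 = 0.857 | 68.6% |
| 10 | 30/40 = 0.75 | 60% |
| 30 | 30/60 = 0.50 | 40% |

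**Step 4: the 5% cut-off in Table 3.02.** An event in k subjects drops out when k/(n+s) < 0.05, that is, when s > 20k − n.
- k = 2, n = 30: 2/30 = 6.7%. At s = 10 it is exactly 5.0% and stays; at s = 11, 2/41 = 4.9% and it drops out.
- k = 2, n = 35 (all five replacements used): 2/35 = 5.7%. It drops out at s = 6, 2/41 = 4.9%.
- k = 3, n = 30: it drops out only at s = 31, 3/61 = 4.9%.

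The cut-off effect is therefore narrow. An event that drops out of Table 3.02 still appears in Tables 3.01 and 3.03 and in the AE listing.

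**Step 5: what is not affected.** Non-serious AE counts do not change. The primary group comparisons use only subjects with an evaluable sample (final SAP section 7.1.1), so screen failures cannot enter them.

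**The case against.** **Intent.** The layout of the final SAP suggests that Safety was meant to lie within Enrolled. Screen failures are reported on Screened (Table 1.02, Listing 1). Tables 1.05 to 1.09 run on Safety while the matching Listings 7 to 10 run on Enrolled, so under the literal rule those tables could contain people missing from their own listings. This is fair evidence of intent, but it does not change the rule to be programmed. The interim-analysis SAP also points the other way: its section 6.1 includes reasons for screen failure among displays based on Safety by default.

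**Study procedures.** The dilution depends on reading that term as Day 1 procedures, although protocol section 6.1 also speaks of screening procedures. The narrow reading is better supported. Section 5.3 spells out which procedures are meant, and section 6.7.1.1 sends occurrences between consent and the start of procedures to medical history.

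**Visibility.** Table 1.04 and Listing 6 would reveal a Safety count larger than Enrolled, and a reader could recalculate. That stands, but it does not correct the printed percentages.

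**Stronger readings.** A reader might infer four things that the documents do not support:
- *The AE percentages will be too low.* That depends on s, which is not given.
- *Table 1.05 would include people with no blood data.* Screening blood is drawn; what they lack is blood collected for cell isolation, and a biopsy.
- *The SAE table will be contaminated.* Sections 5.3 and 6.7.1.1 provide for SAEs from consent. However, section 11.3.1 ties an AE to study procedures in time, and section 11.3.2 says that an event that is not an AE cannot be an SAE. Whether a screen failure's event qualifies is unsettled.
- *The safety endpoint is miscounted.* It is a number of events following biopsy, and could change only through such an SAE.

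**Conclusion.** The Safety rule is wrong as written: applied literally, it gives the AE tables and Table 1.05 a denominator that does not match the question. Severity is low to moderate, because only descriptive percentages are involved and the study tests no formal hypotheses.

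The size depends on the number of screen failures counted in Safety. At zero there is no effect; in general the percentages are multiplied by n/(n+s). This rests on two assumptions: that the literal rule is what gets programmed, and that AE collection starts with the Day 1 procedures. The conclusion about the wording is firm. How far the reported tables would actually move cannot be judged from the documents.

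**What to change.** In section 4 of the final SAP, define Safety as: *all Enrolled subjects in whom at least one Day 1 study procedure was started (peripheral blood collection for cell isolation, local anaesthetic for biopsy, fine needle aspirate or core biopsy).*

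- Do not refer to the screen-failure definition in protocol section 5.3. It joins biopsy and blood collection with an *and*, so a subject with blood taken but no biopsy could be both included and excluded. Under the proposed wording that subject stays in Safety, and so does someone who reacts to the anaesthetic before the needle is used.
- Record the definition in SAP section 2.1 as a change from protocol section 8.3.1, and align 8.3.1 at the next amendment if there is one.
- Keep Tables 3.01 to 3.05 and Table 1.05 on the redefined population.
- List any SAE in a subject outside Safety separately, on the Screened population.
- Where the number biopsied differs from the Safety N, give it in a footnote.

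The cost is one sentence, one note, a change to the Safety flag, one short listing and a conditional footnote. No new data are needed, and the primary biomarker comparisons stay as they are.

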4.1. Protocol Deviations

- Important protocol deviations (including deviations related to study inclusion/exclusion criteria, conduct of the trial, patient management or patient assessment) will be summarised and listed.
- Important deviations which result in exclusion from the analysis population will also be summarised and listed. (Please refer to [Appendix 1: Protocol Deviation Management and Definitions for Per Protocol Population](#)).
- Protocol deviations will be tracked by the study team throughout the conduct of the study in accordance with the Protocol Deviation Management Plan (PDMP).
 - Data will be reviewed prior to freezing the database to ensure all important deviations and deviations which may lead to exclusion from the analysis are captured and categorised on the protocol deviations dataset. This dataset will be the basis for the summaries and listings of protocol deviations.
- A separate summary and listing of all inclusion/exclusion criteria deviations will also be provided. This summary will be based on data as recorded on the inclusion/exclusion page of the eCRF.
- Analyses may be repeated on the Per Protocol population if deemed important.

5. CONSIDERATIONS FOR DATA ANALYSES AND DATA HANDLING CONVENTIONS

5.1. Study Treatment & Sub-group Display Descriptors

Treatment Descriptions			
RandAll NG		Data Displays for Reporting	
Code	Description	Description	Order [1]
A	No Treatment	No Treatment	n/a

NOTES:

1. Order represents treatments being presented in TFL, as appropriate.

Study Group Descriptions			
RandAll NG		Data Displays for Reporting	
Code	Description	Description	Order [1]
1	Healthy Volunteers	Healthy Volunteers	1
2	NOT1D	NOT1D	2

5.2. Baseline Definitions

For all endpoints, the baseline value will be the latest pre-biopsy assessment with a non-missing value, including those from unscheduled visits. If time is not collected, Day 1 assessments are assumed to be taken prior to biopsy and used as baseline.

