6.7.4. Vital Signs

Vital signs will be measured in semi-supine position after approximately 5 minutes rest and will include temperature, systolic and diastolic blood pressure and pulse rate. These will be recorded in the CRF.

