5.3. Change from Baseline Definitions

Definition	Reporting Details
Change from Baseline	=Post-Biopsy Value – Baseline
% Change from Baseline	= $100 \times [(Post\text{-}Biopsy Value - Baseline) / Baseline]$

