10.2. Appendix 2: Schedule of Activities

10.2.1. Protocol Defined Time & Events

Screening procedures in addition to those listed below are (outpatient visit): Informed consent; Inclusion / Exclusion criteria; demography.

Procedure	Screening (between - 56 to 7 days prior to study session)	Study Session Day 1			Telephone follow-up Day ~2 to ~ Day 4	Telephone follow-up Day ~7 to Day ~14	Notes
		Pre biopsy	Biopsy	End of study session visit			
Full physical exam	X						To be completed if a post study visit is required. Attendance to the unit post study sessions only if necessary (at discretion of investigator)
Medical history / Past and current medical conditions	X	X					To be completed if a post study visit is required. Attendance to the unit post study sessions only if necessary (at discretion of investigator)

Procedure	Screening (between - 56 to 7 days prior to study session)	Study Session Day 1			Telephone follow-up Day ~2 to ~ Day 4	Telephone follow-up Day ~7 to Day ~14	Notes
		Pre biopsy	Biopsy	End of study session visit			
Laboratory assessments	X ¹	X ²					To be completed if a post study visit is required. Attendance to the unit post study sessions only if necessary (at discretion of investigator). 1. Blood testing in fasted condition at screening 2. Haematology and clinical chemistry only on Day 1 in a non fasted condition
Concomitant medication review	X	X			X	X	
Alcohol Urine Test and Test for Drugs of Abuse	X	X					
Urine Pregnancy test (in women of child bearing potential)	X	X					

CONFIDENTIAL

203158

Procedure	Screening (between - 56 to 7 days prior to study session)	Study Session Day 1			Telephone follow-up Day ~2 to ~ Day 4	Telephone follow-up Day ~7 to Day ~14	Notes
		Pre biopsy	Biopsy	End of study session visit			
Vital signs	X	X		X			To be completed if a post study visit is required. Attendance to the unit post study sessions only if necessary (at discretion of investigator)
Proposed biopsy site review		X					
Peripheral blood collection for cell isolation		X					
Peripheral blood collection for genetics		X					Optional in consenting subjects
Inguinal lymph node biopsy (fine needle aspirate & core biopsy)			X				
Wound assessment				X	X (telephone)	X (telephone)	To be completed if a post study visit is required. Attendance to the unit post study sessions only if necessary (at discretion of investigator)

CONFIDENTIAL

203158

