10.4. Appendix 4: Derived and Transformed Data

10.4.1. General

Multiple Measurements at One Time Point

 Mean of the measurements will be calculated and used in any derivation of summary statistics but if listed, all data will be presented. Subjects having both High and Low values for Normal Ranges at any post-baseline visits for safety parameters will be counted in both the High and Low categories of “Any visit post-baseline” row of related summary tables. This will also be applicable to relevant Potential Clinical Importance summary tables.
Study Day

 Calculated as the number of days from date of biopsy : 
 Ref Date = Missing → Study Day = Missing Ref Date < Biopsy Date → Study Day = Ref Date – Biopsy Date Ref Date ≥ Biopsy Date → Study Day = Ref Date – (Biopsy Date) + 1

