10.10.6. Safety Tables

Safety : Tables					
No.	Population	IDSL / TST ID / Example Shell	Title	Programming Notes	Deliverable [Priority]
Adverse Events (AEs)					
3.01	Safety	AE1	Summary of Adverse Events Summary by SOC and PT		SAC
3.02	Safety	AE15	Summary of Common (>=5% incidence) Non-Serious Adverse Events by SOC and PT (No. of Subjects and occurrences)		SAC
3.03	Safety	AE5A	Summary of All Adverse Events by Maximum Intensity by System Organ Class and Preferred Term		SAC
Serious Adverse Events					
3.04	Safety	AE16	Summary of Serious Adverse Events by SOC and PT (No. of Subjects and occurrences)		SAC
3.05	Safety	AE1	Summary of Adverse Events Leading to Withdrawal from Study by SOC and PT		SAC
Vital Signs					
3.06	Safety	VS1	Summary of change from baseline in Vital Signs		SAC
3.07	Safety	VS7	Summary of Vital Sign Results Relative to Potential Clinical Importance (PCI) Criteria Post- Baseline Relative to Baseline		SAC

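### The final SAP's default for untimed Day 1 assessments has no exception for end-of-session vital signs, so, read literally, it can leave Tables 3.06 and 3.07 without a scheduled post-biopsy change

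*SAP*

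**What the plan says.** The SAP file holds an interim plan and a later final plan. This point concerns the final plan.

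Section 5.2 of the final plan says that, for all endpoints, "the baseline value will be the latest pre-biopsy assessment with a non-missing value, including those from unscheduled visits". It then adds: "If time is not collected, Day 1 assessments are assumed to be taken prior to biopsy and used as baseline". The interim plan's baseline definition (its section 10.3.2.1) has only the latest-pre-biopsy rule; the missing-time default is new in the final plan.

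Section 5.3 defines change from baseline as "Post-Biopsy Value – Baseline". Section 10.10.6 plans two vital-sign tables on the Safety population: Table 3.06, "Summary of change from baseline in Vital Signs", and Table 3.07, which sets post-baseline results against the criteria for potential clinical importance.

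On how vital signs are captured, Protocol 6.7.4 lists temperature, blood pressure and pulse and says only: "These will be recorded in the CRF". Neither document says whether a clock time is collected.

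**The concern.** The default depends on one thing only: whether a time was collected. It does not ask whether the assessment was scheduled before or after the biopsy. That is harmless for an assessment made once on Day 1, before the procedure. Vital signs are different, because they are taken on both sides of the biopsy on the same day. If the default captures the second reading, the one value that could show a post-procedure change is relabelled as baseline.

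At stake are the planned tabular summaries of vital signs after the biopsy. They support the secondary objective on safety and tolerability, although the stated endpoints for that objective are adverse event counts and questionnaire data.

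**Working it through.** The documents give no figure to reproduce on this point, so the check traces the rule through the schedule and the displays.

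**Step 1. When vital signs are taken.** In the time and events tables (Protocol 6.1; final SAP 10.2.1), vital signs are marked at screening, Day 1 pre-biopsy and Day 1 under the column "End of study session visit". Neither telephone follow-up has a mark. Each subject therefore has exactly one scheduled post-biopsy set, and it falls on Day 1.

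**Step 2. What else the default touches.** Day 1 laboratory tests and blood collection are scheduled pre-biopsy only, so for them the default agrees with the schedule. The final SAP lists laboratory results but plans no laboratory change tables. Tables 3.06 and 3.07 are its only planned displays of change from baseline.

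**Step 3. Apply 5.2 literally to a subject with no vital-sign times.**
- Both Day 1 readings are assumed pre-biopsy.
- Baseline is the latest of these, which by visit order is the end-of-session reading.
- Section 5.3 needs a post-biopsy value. The number of scheduled ones left is 1 − 1 = 0.
- SAP 10.3.2 keeps unscheduled visits out of summary tables, so an extra clinic visit cannot fill the gap.

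**Step 4. Size.** Protocol 4.2 allows up to 15 + 15 = 30 evaluable subjects. If the CRF has no time field, up to 30 of 30 lose their scheduled change. If times are missing for only some, those subjects drop out and the table's n falls. If times are always present, 0 are affected.

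**Step 5. Illustration.** The values are assumed: systolic pressure 125 mmHg before the biopsy and 100 mmHg at the end of the session.

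| Handling | Baseline | Post-biopsy value | Change | Meets the 20 mmHg decrease criterion (SAP 10.6.2)? |
|---|---|---|---|---|
| Classified by planned time point | 125 | 100 | 100 − 125 = −25 | Yes |
| 5.2 literally, no times | 100 | none | not computed | No |

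The absolute lower limit for systolic pressure in SAP 10.6.2 is 85 mmHg. A reading of 100 does not cross it, so in this example only the change criterion would have raised a flag.

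**The case against.** The strongest reply is that the SAP already separates the two readings. Section 10.3.2 makes planned time the default for summaries and derived parameters, and baseline is a derived parameter. The planned time points for vital signs are distinct columns. The second sentence of 5.2 can also be read as a fallback for Day 1 data whose order relative to the biopsy is unknown. A reading that empties two tables the same SAP plans is hardly what its authors intended. All of this has force, and a careful programmer may well reach the right result. What remains is that 10.3.2 gives way where something else is stated. Section 5.2 is a specific statement covering all endpoints, and it refers neither to planned time nor to scheduled post-biopsy assessments. The two sections need to be reconciled in the text.

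Three stronger readings are tempting, and the documents do not support them.

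- **That changes would be diluted by averaging the two Day 1 readings.** A reader might infer this from SAP 10.4.1: "Mean of the measurements will be calculated and used in any derivation of summary statistics". That rule is for multiple measurements at one time point. Pre-biopsy and end of session are two scheduled time points, and 5.2 takes the latest value, not a mean.
- **That a post-procedure change would vanish from the report.** Listing 19 gives all vital signs. Listing 20 covers subjects with any value of potential clinical importance, and some of those limits need no baseline. Protocol 11.3.1 makes clinically significant vital-sign abnormalities, including worsening from baseline, reportable as adverse events, which are tabulated separately. If no times existed for anyone, the tables would also be visibly empty.
- **That the loss will occur.** It depends on a CRF detail that the documents do not give.

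**Conclusion.** The point holds in conditional form. Two conditions must both be met: vital-sign clock times are not collected, and 5.2 is applied literally over the planned-time convention in 10.3.2. The end-of-session reading then serves as baseline, and Tables 3.06 and 3.07 have no scheduled post-biopsy change for the subjects affected, from some up to all of the 30 evaluable. If either condition fails, the effect is nil.

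The wording of 5.2 is certain; whether the loss would occur is not, so confidence overall is moderate. The impact is limited to two descriptive safety tables in an exploratory study without an investigational drug. The flow cytometry comparisons do not depend on this rule. It is still worth correcting, because a stated rule gives the wrong classification in the only tables where change from baseline is planned.

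**What to change.** Reword SAP 5.2 in three respects:

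1. Classify Day 1 assessments by planned time point, pre-biopsy or end of session.
2. Apply the missing-time default only to assessments whose planned time point is pre-biopsy.
3. State that end-of-session vital signs are always post-biopsy.

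A cross-reference to the planned-time convention in 10.3.2 would remove the remaining ambiguity. The cost is a sentence or two in the SAP and one line in the baseline derivation. No new data are needed, because the schedule already distinguishes the two readings.
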